5.1.6. Missing data

If the missing date and month needs to be imputed, they will be imputed in accordance with the imputation rules of Hengrui date-type data. If not recorded in events, the time-event data will be right-censored. See appendix for information on how to judge censoring and calculate censored date. Other missing data will not be handled.

5.2. Study Subjects

Demographics and baseline characteristics will be analyzed based on FAS, and medical history and prior therapy will be analyzed based on SS.

5.2.1. Disposition of subjects

The number of screened subjects, number of enrolled subjects, number and percentage of treated subjects, number and percentage of subjects in the analysis sets, number of subjects who discontinue study/treatment, and number and percentage of corresponding subjects to the reasons for discontinuation.

5.2.2. Demographics and baseline characteristics

Age, gender, ethnicity, height, IPS score, B symptoms, and the occurrence of pulmonary involvement and mediastinal lesions of the subjects are summarized using descriptive statistics, respectively. Continuous variables such as age and body height are summarized using descriptive statistics, such as number of evaluable subjects (n), mean and standard deviation, median, min and max. Categorical variables such as gender and ethnicity will be summarized using descriptive statistics, including number of evaluable subjects per category and corresponding percentage in total population.

5.2.3. Medical history

The analysis of tumor diagnosis includes time to first pathological diagnosis, pathological classification, and Ann Arbor staging.

5.2.4. Prior therapy and concomitant medication

The analyses of previous therapies include time from the last dose to enrollment (< 3 months, 3–6 months, > 6 months), previous therapies (brentuximab vedotin, autologous stem cell transplant, and radiotherapy), and analysis of chemotherapy history (chemotherapy and autologous stem cell transplant) which includes the number of therapy line (1, 2, 3, 4, ≥ 5) and baseline disease status (relapsed/refractory). These analyses will be summarized using frequency and percentage. The number of therapy line (continuous variable) and time from the last dose to enrollment (month) will be summarized using descriptive statistics, such as mean, standard deviation, median, min, and max.

All prior concomitant medications, concomitant medications, and concomitant non-drug therapy will be listed.

5.2.5. Protocol deviations

Before database lock, data of all subjects on CRF will be checked for important protocol deviations. All potential important protocol deviations will be reviewed and evaluated by the investigator and the sponsor.

All important protocol deviations will be summarized and described by type and tabulated for analysis.

Important protocol deviations include but are not limited to the following:

- Serious violation of the inclusion/exclusion criteria;
- Meeting the withdrawal criteria but the subject did not withdraw from the study;
- Use of medication prohibited by the protocol.

5.3. Treatment Compliance

The use of investigational drug during the treatment period is summarized using descriptive statistics by cycles. All study drugs will be listed by subject code, treatment stage, dosing date, and use of medications.

5.4.1. Exploratory analyses

None.

5.4.2. Subgroup analysis

The ORR analysis will be based on FAS. The ORR in subgroups and the corresponding 95% confidence interval will be analyzed. See 5.1.4 for subgroups and the definitions.

5.4.3. Other analysis

None.

5.5. Safety Analyses

All safety analyses will be conducted based on SS.

5.5.1. Extent of exposure

Duration of drug exposure and number of doses received will be summarized.

5.5.2. Adverse events

TEAE is any adverse event after treatment with the investigational drug. AEs will be summarized using descriptive statistics according to Hengrui's Statistical Analysis Reporting Standards, including but not limited to:

- Overview of AEs (of all causes and treatment-related);
- Summary of SAEs;

- Incidence and severity of AEs (of all-cause and treatment-related);
- Causality assessment of AEs;
- Analysis of adverse events of special interest (AESIs).

AESIs mainly include the following:

- Haemangioma (time to onset and duration)
- Grade ≥ 3 infusion reaction
- Grade ≥ 2 diarrhoea/colitis, uveitis, interstitial pneumonia
- Grade ≥ 3 other immune-related adverse events: skin, digestive tract, lungs, endocrine (by system organ class)
- Hepatic enzyme abnormalities: ALT, AST and total bilirubin are abnormal against baseline
- Grade 4 amylase or lipase increased.

For AEs occurring after the start of study treatment, treatment-related AEs include those whose causality with the investigational drug is related, possibly related, unlikely related, or unassessable; if the causality assessment is missing, then the AE will be deemed treatment-related for analysis.

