10.1.3. Determination of the relationship between AEs and investigational drug

AEs will be collected from the signing of the informed consent form to 90 days after the last study dose or the start of new anti-tumor treatment, regardless of whether the event is related to the investigational drug or whether any medication is taken against the AE. From 30 days after the end of treatment, for non-serious AEs, only those related to the investigational drug will be collected. Any discomforts complained by the subject or changes in objective laboratory measurements during the treatment period should be faithfully recorded. The severity, duration, measures taken, and outcome of AEs should also be documented. The study physician should comprehensively assess the relationship between the AE and the investigational drug by considering the temporal relationship between the administration of investigational drug and the occurrence of AE, the characteristics of the investigational drug, the toxicological and pharmacological effects of the investigational drug, concomitant medications, underlying

diseases, medical history, family history, as well as dechallenge and rechallenge. The causality assessment will be provided using the following five categories: "related, possibly related, unlikely related, not related, and unassessable". Events that are assessed to be "related", "possibly related", and "unassessable" will be listed as adverse drug reactions. When calculating the incidence of AEs, the total of these three categories will be used as the numerator and the total number of subjects for safety assessments will be used as the denominator.

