12.5.3. Handling of missing data

Except for missing dates in this study, missing data will not be processed. PFS and other time to event data will be judged according to Hengrui's censoring rules and the censoring time will be calculated. Missing date will be processed according to Hengrui's missing date imputation criteria.

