1. REVISION

Updated to Version 3.0 on 30 Aug. 2020. Formulated with reference to the protocol No. SHR-1210-II-204 (Version 3.0, 19 Jul., 2017).

Content	Before	After
Cover	1. The version number is 2.0 2. The version date is 4 Apr., 2018	1. The version number is 3.0 2. The version date is 30 Aug., 2020
Definition of FAS	
Full Analysis Set (FAS): eligible subjects who have received the investigational drug and meet the following requirements.
 
(1) Subjects who have received rescue autologous stem cell transplant after chemotherapy, and then have recurrence or progression;
 
(2) Subjects who have not received autologous stem cell transplant are required to have received the following treatment:
 
The first-line chemotherapy must be systemic multi-drug combination chemotherapy. For subsequent chemotherapy, it is required that at least one line of chemotherapy is systemic multi-drug combination chemotherapy.
 
Patients with refractory disease are patients who did not achieve PR after ≥ 2 treatment cycles or CR after ≥ 4 treatment cycles, or patients who developed progressive disease, regardless of number of treatment cycles.
 
Patients with relapsed disease are patients who were recently treated with at least second-line chemotherapy prior to recurrence.
	Full Analysis Set (FAS): eligible subjects who have received the investigational drug.
5.1.4 Covariates and subgroups	Subjects who received the highest number of lines of prior chemotherapy or autologous stem cell transplant but achieved non-CR/non-PR are classified as subjects with refractory diseases, and others are classified as subjects with relapsed diseases.	
Relapsed: Best overall response to the last chemotherapy/transplant is CR or PR, and time from the end of chemotherapy/transplant to progression is > 6 months.
 
Refractory: 1. Best overall response to the last chemotherapy/transplant is CR, PR, or not evaluated, and time from the end of chemotherapy/transplant to progression is ≤ 6 months. Or, 2. Best overall response to the last chemotherapy/transplant is PD or SD.
 
Missing: Response to the last chemotherapy/transplant is not evaluated, and time from the end of last chemotherapy/transplant to progression is > 6 months.

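### SAP 5.5.2 counts 'unlikely related' events as treatment-related without noting that protocol 10.1.3 uses three causality categories, and does not expressly commit to the three-category incidence

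*SAP*

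**What the plan says.** Protocol section 10.1.3 has investigators assign each adverse event to one of five causality categories: related, possibly related, unlikely related, not related, unassessable. It then groups them: "Events that are assessed to be 'related', 'possibly related', and 'unassessable' will be listed as adverse drug reactions". For the incidence calculation, "the total of these three categories will be used as the numerator". The denominator is everyone assessed for safety.

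Protocol section 12.5.5 plans incidence and severity tables for all-cause and for treatment-related events. It does not define treatment-related and does not refer back to 10.1.3.

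SAP section 5.5.2 plans the same kinds of table and does give a definition. For events after the start of study treatment, "treatment-related AEs include those whose causality with the investigational drug is related, possibly related, unlikely related, or unassessable". Its list of outputs also names a causality assessment of AEs, with no further detail.

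SAP section 1 says the SAP was written against protocol Version 3.0 of 19 July 2017, the version that contains the three-category rule.

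**The concern.** Two documents in force together give different lists of causality categories for the drug-attributed incidence of adverse events, and neither acknowledges the other. A reader who takes the meaning from protocol 10.1.3 and then reads tables built under SAP 5.5.2 would misread them: some subjects counted as having a treatment-related event may have had only events that the investigator judged unlikely to be related.

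The trial has a single arm, so no control group helps to separate drug effects from background disease. Attribution then rests largely on the investigator's causality call, and readers need to know which calls are in the numerator. The SAP text also does not expressly commit to producing the incidence that the protocol prespecified.

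**Working it through.** There is no stated figure to reproduce. The check compares the two definitions and works out what the difference can do to a rate.

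**Step 1. Categories side by side.**

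| Causality category | Protocol 10.1.3 numerator | SAP 5.5.2 treatment-related |
|---|---|---|
| Related | yes | yes |
| Possibly related | yes | yes |
| Unassessable | yes | yes |
| Unlikely related | **no** | **yes** |
| Not related | no | no |

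Three of five categories count under the protocol and four of five under the SAP.

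**Step 2. Is the difference explained anywhere?** The SAP revision table covers the cover page, the FAS definition and the relapsed/refractory definition. It compares SAP versions, not the SAP with the protocol, so its silence proves nothing by itself. The SAP's safety endpoint section (4.2), the rest of its safety analysis section (5.5) and its appendix do not mention the difference either.

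**Step 3. Direction and size.** Take events after the start of treatment. Let A be the Safety Set subjects with at least one event in the protocol's three categories, B those with at least one 'unlikely related' event, and N the size of the Safety Set.

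- Three-category incidence = |A| / N
- Incidence with the fourth category added = |A or B| / N
- Difference = k / N, where k is the number of subjects in B but not in A

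Since k cannot be negative, the SAP's overall rate is equal to or higher than the three-category rate. The documents do not give k. Assuming all 60 planned subjects enter the Safety Set:

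| k | Difference in percentage points |
|---|---|
| 0 | 0 |
| 1 | 1/60 = 1.67 |
| 3 | 3/60 = 5.00 |
| 6 | 6/60 = 10.00 |

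These values of k are illustrations, not estimates.

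**Step 4. Can the three-category rate be recovered from a table by category?** Not by addition. A subject with one possibly related and one unassessable event appears in both rows. Adding the rows gives 1 + 1 = 2, but the subject contributes 1 to the numerator. The rate needs its own subject-level flag, which can be derived from data already collected.

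**The case against.** **The terms differ.** Protocol 10.1.3 defines adverse drug reactions and SAP 5.5.2 defines treatment-related AEs. The two outputs could coexist, and nothing in the SAP withdraws the protocol's grouping. This stands in part: a straight contradiction is an inference. But 10.1.3 is the only place where the protocol links causality category to a numerator, so it is the only rule a reader of protocol 12.5.5 can apply.

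**The SAP may revise the protocol.** Protocol 12.2 allows this, so the wider definition may be intended. A reader might infer that an amendment was required, because 12.2 asks for one when main or key factors change, and adverse events are listed under the secondary endpoints. The documents do not settle that. Treatment-related incidence is not itself named as an endpoint, and the only decision rule (12.3) concerns ORR. Permission to revise does not, however, make an unstated revision clear.

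**The breakdown may be produced anyway.** The causality item in SAP 5.5.2 sits in an open-ended list governed by the sponsor's reporting standards, which are not among the documents. This stands: one can say only that the SAP text does not expressly commit to the three-category rate.

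**The SAP's rule is open and conservative.** This also stands. A reader might infer that the SAP distorts the safety picture. The definition is printed in full, it cannot lower the overall treatment-related rate, and all-cause tables are planned as well.

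**Missing causality.** SAP 5.5.2 also says that "if the causality assessment is missing, then the AE will be deemed treatment-related for analysis". A reader might see a conflict with the general statements that missing data other than dates are left alone (protocol 12.5.3, SAP 5.1.6). The documents do not support that as a fault: a specific, explicit and conservative rule governs over a general one, and protocol 10.1.3 is silent on missing causality.

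**Conclusion.** The point holds as an unreconciled difference in definition with a limited effect. The SAP's overall treatment-related incidence can only equal or exceed the protocol's three-category incidence. The gap is 1.67 percentage points per subject who qualifies solely through 'unlikely related' events, if all 60 planned subjects are in the Safety Set. How many such subjects there are is unknown, and there may be none.

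The verdict assumes that the protocol's adverse-drug-reaction numerator and the SAP's treatment-related numerator serve the same purpose, and that the protocol's safety denominator is the Safety Set. Toxicity is not understated, and ORR is unaffected.

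A reader might conclude that the SAP's main definition must be narrowed to three categories. The documents do not require this: protocol 12.2 leaves room for the wider rule. Narrowing the main definition in an open-label trial, in a SAP dated August 2020 and so after the anticipated completion of December 2019, would be debatable, because it could only lower the headline rate or leave it unchanged. What is needed is disclosure and the second rate.

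**What to change.** Reconcile protocol 10.1.3 and SAP 5.5.2 as follows:

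1. Add a sentence to SAP 5.5.2 stating that its treatment-related definition departs from the protocol 10.1.3 grouping by including 'unlikely related' events, with the reason.
2. Add the subject incidence under the protocol's three categories, overall and by severity, on the Safety Set, beside the wider rate.
3. Label each table with the definition it uses.

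The cost is one sentence, one derivation flag and one extra table. No new data are needed. The only drawback is that readers see two drug-attributed rates, which the labels should keep apart.

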5.5.3. Laboratory evaluations

The baseline is defined as the last measurement before the first dose. Data will be summarized using descriptive statistics according to Hengrui Statistical Analysis Reporting Standards, including but not limited to:

- Incidence of abnormal measurements and parameters;
- Shift tables and listings of changes in measurements, visits, and parameters from baseline (normal/abnormal).
- Shift tables of CTCAE grades before and after treatment.

Listings of abnormal laboratory will be provided.

5.5.4. Vital signs

The baseline is defined as the last measurement before the first dose. Data will be summarized using descriptive statistics according to Hengrui Statistical Analysis Reporting Standards, including but not limited to: descriptive statistics and categorical analysis of absolute values and changes from baseline at scheduled visits in the protocol. Blood pressure and heart rate will be summarized. See Appendix B for classification criteria.

5.5.5. ECG

ECG results will be listed.

5.5.6. Physical examination

Data will be summarized using descriptive statistics according to Hengrui Statistical Analysis Reporting Standards, including but not limited to: descriptive statistics of absolute values at scheduled visits in the protocol.

5.5.7. Other safety measures

Baseline ECOG PS and post-baseline changes will be summarized by visit. B symptom scores will be summarized by visit and analyzed using frequency and percentages (according to categorical variables).

Echocardiography results will be listed.

5.6. Pharmacokinetic Analysis

PK analysis is provided by the vendor and not included in this SAP.

5.7. Pharmacodynamics Analysis

Not involved.

5.8. Other Analysis

None.

6. INTERIM ANALYSIS

No routine interim analysis.

8. APPENDIX

Appendix 1.1. Definition of progression-free survival (PFS).

No.	Situation	Date of Progression/ Censoring	Handling
1	No baseline assessment	Date of first dose	Censoring
2	No post-baseline assessment, and no death	Date of first dose	Censoring
3	Any death (except #5)	Date of death	Event
4	Progressive disease during study (including after missing one assessment)	Date of progressive disease	Event
5	Death or progressive disease after 2 consecutive missing tumor assessments	Date of last tumor assessment before missing	Censoring
6	Withdrawal from the study due to toxicity or other reasons without PD or death record	Date of last tumor assessment before study withdrawal	Censoring
7	No progressive disease or death recorded before the initiation of new anti-cancer treatment	Date of last recorded objective tumor assessment as no PD before the initiation of new anti-tumor treatment	Censoring

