9. ASSESSMENTS

9.1. Assessment of Efficacy

The Lugano 2014 criteria are used to evaluate the objective response rate (ORR), including the CR and PR cases.

ORR: Defined as the proportion of subjects whose best response reaches CR or PR from the first dose to the occurrence of PD or the start of new anti-tumor treatment, whichever comes first

PFS: Defined as the time from the date of the first dose to the first documented PD or all-cause death, whichever occurs first. If the subject has not had PD or died by the data cut-off date, the cut-off date is the date of the subject's last efficacy evaluation. If the subject has not received tumor evaluation, the cut-off date is the date of the first dose, and PFS lasts for 1 day.

DoR: Defined as the time from the date of the first CR or PR to the date of initial assessment of PD or all-cause death, whichever comes first. If the subject has not had PD or died by the data cut-off date, the censoring date is the date of the subject's last efficacy evaluation. Only applicable to subjects with CR/PR.

TTR: Defined as the time from D1 of administration to the first evaluation of PR or CR, whichever comes first. Only applicable to subjects with CR/PR.

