12.2. Statistical Analysis Plan

Statistical summaries and analytical methods of data collected from this study will be detailed in another individual statistical analysis plan (SAP). The finalized SAP will be kept by the sponsor. This SAP may contain revisions to the relevant contents in the protocol. However, when the revised content involves the main and/or key factors in the protocol, such as the definition of endpoints and the corresponding analysis, such a revision should be reflected in the protocol amendment version.

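### SAP Appendix 1.1 gives some subjects two opposite PFS outcomes with no row order, and censors some progressions and deaths that protocol 9.1 counts as events

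*SAP*

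**What the plan says.** Protocol 9.1 defines PFS as "the time from the date of the first dose to the first documented PD or all-cause death, whichever occurs first". Its censoring rule has one condition: "If the subject has not had PD or died by the data cut-off date". The PFS definition contains no rule for missed scans or for new anti-tumor treatment; the new-treatment limit in that section belongs to ORR. Protocol 12.5.3 says that time-to-event data follow the sponsor's censoring rules, but does not set them out. SAP 5.1.6 sends the reader to the appendix for censoring.

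The rows of SAP Appendix 1.1 that matter here are:

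- Row 1: no baseline assessment, censored at first dose. Unlike row 2, it does not require that the subject is alive.
- Row 3: "Any death (except #5", an event at the date of death.
- Row 4: "Progressive disease during study (including after missing one assessment", an event at the date of PD.
- Row 5: "Death or progressive disease after 2 consecutive missing tumor assessments", censored at the last assessment before the gap.
- Row 7: "No progressive disease or death recorded before the initiation of new anti-cancer treatment", censored at the last PD-free assessment before the new treatment.

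Neither the table nor SAP 5.1.6 ranks the rows. Protocol 12.2 adds that if the SAP revises main or key factors, such as endpoint definitions, "such a revision should be reflected in the protocol amendment version". The SAP (30 August 2020) still refers to protocol Version 3.0 (19 July 2017).

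**The concern.** A censoring table should send each subject to one outcome. Here some subjects fit an event row and a censoring row together, so two programmers working correctly from the same table could produce different PFS data. The case is realistic. Scheduled imaging stops when new anti-tumor treatment starts (protocol 8.2), but survival follow-up continues every 3 months, so deaths after a switch of therapy will be recorded.

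The table also departs from protocol 9.1, because known progressions and deaths become censored times. If subjects who miss scans or switch therapy are doing worse than those who stay on schedule, that censoring is informative and lengthens estimated PFS. The trial has one arm, so no control group shares the bias, and no planned analysis shows its size.

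**Working it through.** **1. The plan's own figure.** The only power statement concerns ORR. With 50 subjects, 28 responders is the smallest count with a Clopper-Pearson lower limit above 40% (28/50 gives 41.25%; 27/50 gives 39.32%). The exact probability of 28 or more responders at a true ORR of 65% is 92.90%, as stated. PFS plays no part in it, and the plan gives no event count or power for PFS.

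**2. Test subjects run through the table.** Scans are due in Weeks 9, 17, 25, 37 and 49, then every 16 weeks to Week 97 (65, 81, 97), then every 26 weeks (123, 149).

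| Subject | Rows met | SAP handling | Protocol 9.1 |
|---|---|---|---|
| Last scan Week 25, new therapy Week 30 without PD, death Week 45 | 3 and 7 | Event at Week 45, or censored at Week 25 | Event at Week 45 |
| Last scan Week 25, new therapy Week 30 without PD, PD Week 40 | 4 and 7 | Event at Week 40, or censored at Week 25 | Event at Week 40 |
| No baseline assessment, death Week 10 | 1 and 3 | Censored at first dose, or event at Week 10 | Event at Week 10 |
| PD or death after two consecutive missed scans | 5 | Censored at last scan before the gap | Event at PD or death |

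In the first line the two answers differ by 45 − 25 = 20 weeks as well as in status. If that subject dies in Week 50 instead, the Week 37 and Week 49 slots have both passed. If they count as missing, row 5 applies and censors at Week 25, the same as row 7. If they do not, because scans were no longer required, rows 3 and 7 still conflict. The table does not say which. The conflict is therefore clearest for deaths before the second slot.

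**3. How far row 5 moves time back.** Minimum set-back = week of second missed scan − week of last scan. Months = weeks × 7/30.44 (the SAP 5.1.3 divisor).

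| Last scan (week) | Missed scans (weeks) | Set-back (weeks) | Months |
|---|---|---|---|
| 9 | 17, 25 | 16 | 3.7 |
| 25 | 37, 49 | 24 | 5.5 |
| 49 | 65, 81 | 32 | 7.4 |
| 65 | 81, 97 | 32 | 7.4 |
| 81 | 97, 123 | 42 | 9.7 |
| 97 | 123, 149 | 52 | 12.0 |

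Planned follow-up is about 24 to 29 months: 24 months after the last first dose, plus up to five months of enrollment (June to November 2017). Day 1 of Week 123 falls at 122 × 7/30.44 = 28.1 months and of Week 149 at 148 × 7/30.44 = 34.0 months. The 42-week figure can therefore arise only for the earliest subjects, and the 52-week figure needs follow-up beyond the plan.

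**4. Illustration of the effect on the estimate.** All inputs other than n = 60, the follow-up and the scan schedule are assumptions.

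- Exponential PFS, true median 12 months, follow-up 24 to 29 months, 2,000 simulated trials, with affected events recoded as censored 7.4 months earlier. The estimated median moves from about 11.7 months to 12.8 (10% of events recoded) or 14.0 (20%).
- Exponential PFS, true median 52 weeks, cut-off 104 weeks, with affected subjects censored at the last scheduled scan at least 12 weeks before the event. Of about 45 events, 2, 5 or 9 are recoded (5%, 10%, 20%). The median moves from about 51 weeks to 54, 57 or 63, and 52-week PFS from about 50% to 51.5%, 52.8% or 56.3%.

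In the first model about 44% of events fall before 7.4 months and cannot be set back that far. The schedule-based model gives similar shifts, so the assumed fraction drives the result.

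**The case against.** The sponsor has several fair answers.

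- **Delegated censoring.** Protocol 12.5.3 refers to the sponsor's censoring rules, and Appendix 1.1 can be read as carrying them out. A reader might infer that the SAP broke protocol 12.2 by changing an endpoint definition without an amendment. The documents do not establish that: 12.5.3 leaves room for censoring rules beyond 9.1, and 12.2 is limited to main or key factors, which may not include censoring of a secondary endpoint. What stands is that 12.5.3 does not state the rules, so two texts remain that give different outcomes.
- **Literal reading.** Row 3 covers any death and names its only exception, so row 7 could be taken to govern only subjects who do not die. That reading agrees with protocol 9.1, but the table does not state it, and it leaves rows 4 and 7 and rows 1 and 3 overlapping.
- **Small numbers.** With imaging ending at new therapy, PD after a switch will seldom be documented. Eligibility requires a measurable lesion, so a missing baseline assessment should be rare. Subjects who stop treatment without PD stay on the scan schedule, and many deaths in survival follow-up will come after PD has already been counted. All of this stands.
- **Common conventions.** Censoring at new therapy or after two missed scans is usual. Agreed; the fault is the missing order and the unreconciled difference from 9.1.
- **Bias in both directions.** An analysis by 9.1 dates PD at detection, which after a long scan gap also lengthens PFS. That is correct and should be said when the two results are reported.

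**Conclusion.** The point holds. Three kinds of subject receive opposite handling under Appendix 1.1 with no rule to choose between rows. Row 5, and row 7 if it overrides row 3, censor progressions and deaths that protocol 9.1 counts as events. Both findings rest on the text alone.

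The set-back under row 5 is also firm, as it follows from the scan schedule: at least 16 weeks early on, 32 weeks after Week 49 or 65, 42 weeks after Week 81 and 52 weeks after Week 97, subject to visit windows and to follow-up lasting that long. The shift in the median is not firm. A reader might infer from the simulations that PFS will be overstated by one to two months. The documents do not support that, because they give neither a PFS assumption nor the fraction of subjects affected. They also do not say why subjects would miss scans or switch therapy, so the informative nature of the censoring is plausible rather than shown.

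PFS is a secondary, descriptive endpoint with no test or threshold. The ORR decision rule and its 92.90% power are unaffected. The change is worth making because it is cheap and the ambiguity reaches a reported estimate.

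**What to change.** 1. Keep the SAP censoring conventions as the main PFS analysis, but state a priority order for the rows. One workable version: rows 3 and 4 both except rows 5 and 7; row 1 gains the same no-death condition as row 2; and scans no longer required after new therapy do not count as missing. Editing row 3 alone is not enough, since the other two overlaps would remain. Because this version makes the main analysis censor deaths after new therapy, it should be paired with item 2.
2. Add one sensitivity Kaplan-Meier analysis by protocol 9.1, counting the first documented PD or any death as an event on its date, regardless of missed scans or new therapy. Report both medians together, with the number of subjects whose status differs.
3. Reconcile the texts: state in protocol 9.1 or 12.5.3 that the Appendix 1.1 rules apply, or explain in the SAP how they relate to the 9.1 definition.

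The cost is a few edited table rows, a short cross-reference and one further analysis on data already collected. The sensitivity median may be shorter than the main one, and it carries its own bias where PD is found late after a scan gap.
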